## 1.1 PRÉCIS

### Study Title

[figure not shown]
Mindfulness-Based Dementia Care Partner Program to Reduce Depressive Symptoms

### Objectives

1. To assess the feasibility, acceptability, and fidelity of implementation of the MBDC program
2. To determine the feasibility of obtaining clinical outcome measures
3. To assess the willingness of participants to share access to healthcare utilization records

### Design and Outcomes

This study will use a stepped wedge incomplete design with random assignment to accommodate continuous enrollment of participants and a rolling schedule of existing MBDC courses. Course participation includes the voluntary sharing of information through answering questions related to burden and mood as part of an administrative data collected at four points as illustrated below:

### Interventions and Duration

The Mindfulness-Based Dementia Care (MBDC) program is an adaptation of Mindfulness-Based Stress Reduction (MBSR) for CPs of people living with Alzheimer's disease and related dementias. The web-based, group intervention consists of nine sessions including weekly two-hour classes and a half-day retreat. Participants learn from certified instructors how to incorporate mindfulness practices into day-to-day life to help cope with the challenges and stresses of dementia care. Courses currently are part of the memory clinic programs at all three of the pilot sites. Participants will be a part of the study for about 7 months including 8 weeks of intervention, a variable pre-intervention control period, and a 3-month follow-up period.

### Sample Size and Population

130 adult CPs of people living with Alzheimer's disease or related dementia will be recruited to enroll in the MBDC program. Recruitment will occur as part of standard of care in three specialty care memory clinics. Eight or more MBDC courses will be held over the course of one year. During registration, CPs will self-select two options for a preferred day and time to meet for the group class. CPs will be randomly assigned to one of the two preferred day/times to assess the feasibility of randomization in a full scale embedded pragmatic clinical trial.

## **1 STUDY OBJECTIVES**

### **1.1 Primary Objective**

The primary aim of this study is to assess the feasibility, acceptability, and fidelity of implementation of the Mindfulness Based Dementia Care (MBDC) program.

### **1.2 Secondary Objectives**

The second aim of this study is to determine the feasibility of obtaining clinical outcome measures. The third aim of this study is to explore the feasibility of obtaining online consent for research access to care partner (CP) and person living with dementia (PLWD) healthcare utilization records.

## **2 BACKGROUND AND RATIONALE**

### **2.1 Background on Condition, Disease, or Other Primary Study Focus**

[figure not shown]
More than 11 million people provide unpaid care for people living with dementia (PLWD) in the United States. While there are certain positive aspects of being a care partner (CP) and caregiving, coping with the PLWD's progressive loss of memory and ability to function in daily life can be particularly challenging and stressful. The increased burden and chronic stress of caregiving can lead to increased risk of mental health issues, as well as physical health changes. Compared to non-CPs, CPs have been shown to have increased incidence of chronic conditions, including heart disease and hypertension, as well as higher utilization of healthcare services. CPs also experience high rates of anxiety and depression. Increased depressive symptoms are associated with higher CP healthcare utilization. In a recent meta-analysis, depression was prevalent in 34% and anxiety in 44% of CPs of PLWD. The odds of having depression were 1.5 times higher for females than males and 2.5 times higher for spousal CPs.

### **2.2 Study Rationale**

Mindfulness Based Stress Reduction (MBSR) is a group-based, standardized program that is both psychoeducation and skills-based, which uses mindfulness meditation practices to help people better cope with their emotions. MBSR has been studied as a complimentary therapy to reduce stress and manage symptoms in a wide range of conditions including chronic pain, fibromyalgia, cancer, anxiety and depression. Mindfulness based interventions, including MBSR, have been shown to decrease symptoms of depression. MBSR is safe, with no reported adverse events. A recent review focused on the ability of mindfulness-based interventions to support caregivers of older adults, assessing depression, anxiety, burden, stress, and quality of life. Three randomized controlled trials, including a total of 135 CPs, demonstrated lower level of depressive symptoms in MBSR groups compared to active control groups. There was also some evidence for improvements in anxiety, stress, and overall wellbeing. Importantly, MBSR has been tested with the intervention delivered to CPs by community-based instructors. Thus, MBSR has shown Stage III efficacy in the NIH Stage Model for Behavioral Intervention Development and readiness for Stage IV testing.

There are still several challenges to a full-scale study of MBSR in CPs of PLWD including phased enrollment of courses, its lack of dementia and CP specific education and support, and the unavailability of pragmatic clinical outcomes. The Presence Care Project ([www.presencecareproject.com](http://www.presencecareproject.com)), a community-based non-profit organization, has developed a version of MBSR designed specifically for CPs of PLWD called Mindfulness Based Dementia Care. Mindfulness Based Dementia Care (MBDC) is a nine-week group program, which includes both formal and informal mindfulness practice, role play, and lectures, combined with dementia-specific education and CP peer support. MBDC is recognized as a Dementia Care Program on the Best Practice Caregiving website, a partnership between Benjamin Rose Institute on Aging and Family Caregiver Alliance. MBDC participants learn how to incorporate mindfulness practices into day-to-day life as a CP to help cope with the challenges and stresses of dementia care. CPs participating in MBDC make changes to their thinking, becoming more self-aware and mindful. These behavior changes are thought to lead to an increased ability to cope with emotions as measured by decreased depressive symptoms and CP burden (Figure 1).

**Figure 1.** Intervention Framework

MBDC is currently being taught at memory care clinics in the United States by Presence Care certified instructors. The cost of conducting a MBDC course is estimated to be in the range of \$3,000-\$4,000, depending on the site. Healthcare systems have typically supported the cost of instruction through clinic operational funds or philanthropy.

[figure not shown]
### **3 STUDY DESIGN**

**Design:** The overall goal of this proposal is to test the feasibility of implementing MBDC to guide subsequent evaluation of effectiveness of the MBDC intervention in a full-scale embedded pragmatic clinical trial (ePCT). This study will use a stepped wedge incomplete design with random assignment to accommodate continuous enrollment of participants and a rolling schedule of initiating MBDC courses. We aim to examine the effects of MBDC on depressive symptoms and burden in CPs of PLWD. CPs will be referred to MBDC from three healthcare settings and surrounding community partners. MBDC program registration and collection of administrative data will occur via Presence Care's web-based platform. MBDC courses will be taught in groups via web-based video calls by Presence Care certified instructors, including one by an African American trainee. Eight or more courses will be taught over 9 months. Upon registering, CPs will select two preferred days/times for class and will be randomized to one of them. Participants may not be assigned to the instructor at their memory clinic. With up to 15 participants anticipated per course, a total of up to 130 CPs will be enrolled. Administrative data will be collected at the time of registration, prior to the MBDC course, immediately following the MBDC course, and 3 months later (Figure 4). The

administrative data collected will be used as pragmatic outcomes in this study. Participants will be a part of the study for about 7 months including 8 weeks of intervention, a variable pre-intervention control period, and a 3-month follow-up period. We will request a waiver of informed consent for this study. We will also request a partial HIPAA waiver of authorization for use of electronic health record data for recruitment purposes. The administrative data collected by Presence Care is not protected health information; no HIPAA authorization/waiver is required, but the data obtained by the research team from Presence Care for research purposes will be covered by a data use agreement.

**Study population:** The study population consists of CPs of PLWD from three settings. Multiple strategies described below will be used to increase the diversity of CP participating in MBDC.

**Figure 4. Study Design**

**Settings:** The three healthcare settings that will refer CPs to MBDC in this pilot include:

- the HealthPartners Center for Memory & Aging in St. Paul, MN;
- the Ray Dolby Brain Health Center at California Pacific Medical Center, a Sutter Health affiliate in San Francisco, CA; and
- the University of Michigan – Alzheimer’s Disease Research Center in Ann Arbor, MI.

Challenges to conducting ePCTs in CPs include the lack of pragmatically available clinical outcomes and the complexity of collecting and harmonizing data across multiple, diverse healthcare systems. MBDC evaluation data is currently being collected at the three pilot sites in different ways. To overcome these challenges, we will partner with Presence Care to develop and implement a permanent centralized process for MBDC class registration and administrative data collection on their website. This upgraded infrastructure will enable the collection of common administrative data, including questionnaires with clinical outcomes, for long-term use in evaluation of the program.

**Randomization scheme:** At the time of enrollment (registration on the Presence Care site), a CP will be presented with several currently enrolling class options (multiple days/times of week) and asked to select two that work with their schedule. They will then be randomly enrolled in one of the two selected courses, allowing for randomization on the class level while still accommodating the participant’s schedule. If a CP declines the assigned MBDC course, they will be allowed to self-select a course or to withdraw. As randomization is planned for the full-scale ePCT, it is important to determine acceptability of this component of implementation. This is balanced with the health care settings needs to support care partners experiencing stress.

**Intervention Structure and Implementation Protocol:**

MBDC group sessions will be held virtually via web-based video calls. Presence Care certified instructors will facilitate the sessions according to the MBDC protocol. Nine sessions including 8 weekly classes (2 hours each) and a retreat (4 hours) will cover several topics (Table 1). The session taught by the African American instructor may include in-person group meetings in that community church setting.

The core course content for each session will be recorded for individuals who are unable to attend the live session. In this pilot, a phone option for CP participation will also be made available. There is currently a group of MBDC graduate meeting weekly by phone. Many of the CPs participating prefer the phone interaction vs. video call. We will explore whether phone participation increases access for participants with lower socioeconomic status and describe any differences in the intervention fidelity.

Instructors will reach out to CPs that miss class sessions with an email checking in and include a link to the recording. CPs will be asked to watch the session and send the instructor a summary about the content to make up the session. Instructors may withdraw CPs who miss more than 3 sessions. CPs will be mailed one chapter of the MBDC workbook for each class (Appendix 1). The CP workbook is currently available in English for in-person and virtual classes. Presence Care is currently in the process of updating the in-person Spanish MBDC workbook for the virtual class mode. Upon completion of the course, participants will be offered the opportunity to participate in a variety of mindfulness maintenance activities, such as weekly, guided virtual group meetings of MBDC graduates.

The Presence Care website will be upgraded to include a permanent infrastructure for centralized registration and administrative data collection. Data collection will be completed through Research Electronic Data Capture (REDCap) and will include clinical outcomes and program evaluation questionnaires. REDCap is a secure web-based system used for data collection and is compliant with federal regulations (21 CFR Part 11, FISMA, HIPAA, and GDPR). A Presence Care administrator will have access to the entire dataset and each instructor will have access to their participants' data. A data use agreement between Presence Care and HealthPartners Institute will be executed for the research use of data. Through this agreement, the HealthPartners biostatistician will have access to a limited data set through the REDCap portal.

**Data sources, elements, and collection protocol:** Table 2 details the data elements collected. The main data source for this project is the Presence Care administrative database. All CP and PLWD data will be entered by the CP either into the website or given verbally to HealthPartners research support staff over the phone. There will be no

**Table 1. MBDC Session Topics**

CLASS	TOPIC
1	Introduction to Mindfulness-Based Dementia Care -and one another!
2	Attitudinal Foundations & Beginning Practice
3	Living Grief & Self-Compassion
4	Coming to Our Senses
5	Everyday Communication
6	Being with Difficulty
7	(Retreat)
8	Deepening Practice -Day of Mindfulness
9	Caring for Yourself
	Reflecting Backward & Practicing Forward

transfer of data from healthcare settings to Presence Care. All questionnaires will include the same items, with an addendum added to the third questionnaire, which will include course evaluation and a theoretical assessment of willingness to share healthcare utilization data. Our Aim 3 goal is to determine whether CPs will be willing to consent online to share their insurance information evaluate healthcare utilization in future studies. The question would be “In the future, we wish to study how the MBDC affects health care utilization. If we were to do so, would you be willing to provide your Medicare ID number to help us understand how this program affects your health? Please note that we are not asking you to provide this information now, nor are collecting your utilization data.” A second question will ask if they are a legally authorized individual for the PLWD, and if so, would they theoretically consent to also sharing the Medicare ID of that individual. We will not collect the Medicare ID number but ask theoretically if they would consider participating and offer the choices of “yes/no/I don’t know”.

**Table 2.** Data elements collected. All items will be a permanent part of Presence Care administrative data collection.

Data Forms	Time Point Collected	Entered By	Detailed Data Elements
Class Registration	Initial Registration	CP	Name, Address, Date of Birth, Phone Number, Referral Source, Race, Ethnicity, Language, Education, Length of Caregiving, Relationship to PLWD, Preferred Classes, Emergency Contact
		CP (about PLWD)	Name, Type of Residence, Date of Birth, Dementia Diagnosis
Questionnaire 1,2, 3, 4	Initial Registration (Q1), Week before MBDC (Q2), Week after MBDC (Q3), 3 months after MBDC completion (Q4)	CP	Clinical Outcome Scales: Depressive Symptoms (CES-D-10  ) and Caregiver Burden (6-item Zarit Burden Interview, ZBI-6  )
			CP Behavior Change Measures (: Self-Compassion (The State Self-Compassion Scale Short Form, SSCS-S)  and Mindfulness (The 5-Item Mindful Attention Awareness Scale – State)  )
Questionnaire 3 only	Week after MBDC	CP	Course Satisfaction Assessment of willingness to share healthcare claims for CP and PLWD
Presence Care	Throughout MDBC sessions	Instructor	Class assigned, dates of classes, attendance, mode of attendance, instructor name
Automated Information	Throughout MBDC sessions	REDCap	Date of Registration, Date of Questionnaires Completion, Mode of Registration and Collection of Data
Post-Implementation Data	Following completion of all MBDC sessions	Clinic Directors	Healthcare Setting Stakeholder Interviews of Memory Clinic Directors

**Outcomes:** To assess the feasibility, acceptability, and fidelity of implementation of the MBDC program, the Aim 1 outcomes will include: number of CP participants contacted

for recruitment, number of CP enrolled, missingness in the class registration materials, response rate to the four questionnaires, completeness of the administrative generated data, CP attendance and module completion rates. To determine the feasibility of obtaining clinical outcome measures, the Aim 2 outcomes will include response rates and completeness of data for Depressive Symptoms (CES-D-10^22) and Caregiver Burden (6-item Zarit Burden Interview, ZBI-6). To explore the feasibility of CP sharing access to healthcare utilization records, the Aim 3 outcome will include the number of CPs who are express willingness for theoretical use.

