## **4 SELECTION AND ENROLLMENT OF PARTICIPANTS**

### **4.1 Inclusion Criteria**

During the online MBDC registration process, CPs will be asked yes/no questions to determine eligibility based on the inclusion/exclusion criteria. Branching logic within the survey will prompt messaging for those are ineligible and trigger an exit from the registration process. In addition, instructors will confirm eligibility of CPs during the check-in calls.

Participants must meet all the following inclusion criteria to participate in this study

- Age  $\geq 18$  years
- Self-identify as being an informal CP providing caregiving to a PLWD
- Register for an MBDC course through the Presence Care Website

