**Equation 1.**

$$Change_{itk} = \beta_0 + \delta X_{itk} + \omega Pre_{itk} + \beta X_i + \gamma_{0ik} + v_{0k} + \epsilon_{ik}$$

i = Participant Subscript, 1, ..., N

k = Cluster Subscript, 1, ..., K

t = time period, 1 = Control, 2 = Intervention

Changeitk = Change in efficacy outcome over period t

Preitk = Pre measurement from period t

For Control period: Pre = Q1, Change = Q2 - Q1

For Intervention period: Pre = Q2, Change = Q3 - Q1

xitk = Binary indicator for intervention for patient i in k at time t

Xi = Vector of covariates for participant i

$\beta_0$  = General intercept of the model

$\delta$  = Intervention effect (coefficient of xitk)

$\omega$  = Baseline measurement adjustment effect (coefficient of Preitk)

$\beta$  = Vector of coefficients associated with covariates in Xi

$\gamma_{0ik}$  = Participant-specific random intercept with mean zero and variance  $\sigma_{\gamma}^2$

$v_{0k}$  = Cluster-specific random intercept with mean zero and variance  $\sigma_v^2$

$\epsilon_{itk}$  = Random error with mean zero and variance  $\sigma_{\epsilon}^2$

**Aim 3 - Exploratory Feasibility Analysis:** To explore the feasibility of obtaining online consent for research access to CP healthcare utilization records. The number of CPs who agree to access for themselves or the PLWED on Questionnaire 3 will be counted. While we will not specifically collect utilization data, the number of CPs who agree will inform the feasibility of including healthcare utilization as an outcome in a full-scale ePCT. Any differences in CP demographics between enrollees who opt-in and those who opt-out will be assessed.

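### The Aim 3 question cannot separate care partners without Medicare from care partners unwilling to share, so its 'yes' count is hard to interpret

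*Combined protocol and SAP*

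**What the plan says.** Section 3 (data sources, in the text after Table 1) states the purpose broadly: "Our Aim 3 goal is to determine whether CPs will be willing to consent online to share their insurance information". The item itself is narrower. It asks "would you be willing to provide your Medicare ID number to help us understand how this program affects your health", as a hypothetical about a future study. The plan will "ask theoretically if they would consider participating and offer the choices of" yes, no and I don't know. No answer is described for a CP who has no Medicare.

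The companion item about the person living with dementia (PLWD) does carry a filter: "A second question will ask if they are a legally authorized individual for the PLWD, and if so, would they theoretically consent". No filter is described for the CP's own item.

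The people asked are adults of any age. Section 4.1 requires age 18 or over and "Self-identify as being an informal CP providing caregiving to a PLWD". It sets no coverage requirement. Table 2 of Section 3 (data elements) lists date of birth and relationship to the PLWD at registration, but no insurer or Medicare field.

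The outcome is a count. Section 3 says "the Aim 3 outcome will include the number of CPs who are express willingness for theoretical use", and Sections 9.4.2 and 9.5 also count those who agree. Section 9.5 adds "Any differences in CP demographics between enrollees who opt-in and those who opt-out will be assessed", and says that the count will inform whether utilization is feasible as an outcome in the full-scale trial. Table 3 defines denominators for recruitment, completion and questionnaire response, but has no row for Aim 3.

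**The concern.** A future trial that wants CP utilization from Medicare claims needs two facts: what share of CPs hold Medicare, and what share of those would provide the ID. The item measures neither separately. A 'no', an 'I don't know' or a blank may mean reluctance, or may mean that the question did not apply.

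The two explanations call for different action. Low willingness among holders is a consent problem. Low coverage is a data-source problem, and would point to other insurers. Because the question is asked once, on Questionnaire 3, later analysis cannot fully separate them.

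The demographic comparison inherits the difficulty. If coverage differs by age or by relationship to the PLWD, a difference between those who opt in and those who opt out may be a difference in coverage.

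**Working it through.** The plan gives no expected rate, target or denominator for Aim 3, so it has no figure of its own to reproduce. What follows is a sensitivity calculation.

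**Inputs.** From the documents: the item and its three answers (Section 3), eligibility (Section 4.1), the fields collected (Table 2 of Section 3), and enrollment of up to 130 (Section 9.2). Assumed, because the documents do not give them:
- m, the share of CPs holding Medicare: 0.80, 0.60 or 0.40 (that is, 20%, 40% or 60% without).
- w, true willingness to share insurance information: 0.80, taken as the same in holders and non-holders.
- q, the share of CPs without Medicare who answer yes: 0 to 1.

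**Step 1: observed share answering yes.** p = m·w + (1 − m)·q, so the gap from true willingness is p − w = (1 − m)(q − w).

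| q | 20% without Medicare | 40% without | 60% without |
|---|---|---|---|
| 0 | 64% (−16 points) | 48% (−32) | 32% (−48) |
| 0.20 | 68% (−12) | 56% (−24) | 44% (−36) |
| 0.80 | 80% (0) | 80% (0) | 80% (0) |
| 1.00 | 84% (+4) | 88% (+8) | 92% (+12) |

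For example, with 40% without Medicare and q = 0.20: 0.60 × 0.80 + 0.40 × 0.20 = 0.56. The sign of the gap is the sign of q − w.

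**Step 2: the count as a measure of linkable CPs.** The number who hold Medicare and would share is N·m·w. The 'yes' count exceeds it by N(1 − m)q, which is never negative. Take N = 130 with all answering, m = 0.60 and w = 0.80. The linkable number is 130 × 0.48 = 62.4, or about 62. The 'yes' count is the same at q = 0, about 73 at q = 0.20 (130 × 0.56 = 72.8) and 104 at q = 0.80 (130 × 0.80).

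**Step 3: one observed figure, two explanations.** With q = 0, an observed 48% fits m = 1.00 and w = 0.48, and equally m = 0.60 and w = 0.80. The planned data do not distinguish them.

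**Step 4: the demographic comparison.** Take two groups with the same w = 0.80 and q = 0, but m = 0.80 in one and 0.40 in the other. Their 'yes' shares are 64% and 32%. The 32-point difference is all coverage and none of it willingness.

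**Step 5: what the fix recovers.** Restricting to holders gives w in every cell of the table, whatever m and q are.

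**The case against.** A reader might infer that CPs without Medicare are counted as unwilling and that the result is therefore biased downward. The documents do not support that reading, for three reasons.

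- No section says how 'no', 'I don't know' or a blank is classified. The plan counts those who agree. Two groups are to be compared and three answers are offered, but the mapping is not stated.
- A CP without Medicare is not forced into 'no' or 'I don't know'. Section 11.2 allows questions to be skipped, and the survey alert asks for an answer without requiring one. Because the question is hypothetical, such a CP could also answer yes.
- The direction depends on q, which the documents do not give. The 64%, 48% and 32% figures need q = 0. Under that same assumption the 'yes' count equals the number of CPs who hold Medicare and would share, which is a usable yield for planning. If q is above zero, the count overstates that yield.

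Two further points stand. Aim 3 informs the later choice and does not decide it: the analysis is exploratory, and the progression criteria in Section 9.1 rest on attendance and recruitment diversity. Date of birth and relationship are collected, so a pattern by age would be visible.

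These points remove any claim about direction and lower the severity. They do not repair the item. Age is only a proxy for coverage, and neither reading of the count can be confirmed from the data planned.

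**Conclusion.** The point holds as a limit on interpretation. As described, the CP item is narrower than the Aim 3 goal, goes to CPs whether or not they hold Medicare, and has no answer or field that records coverage. A CP without Medicare therefore cannot be distinguished from an unwilling one. The count may understate willingness or overstate the number of linkable CPs, and the opt-in versus opt-out comparison may reflect coverage.

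Any size is conditional on assumed values. At 80% willingness and 20% to 60% without Medicare, the gap runs from −48 points (60% without, no non-holder saying yes) through zero (non-holders say yes at the same rate) to +12 points (60% without, all non-holders saying yes). If every CP held Medicare, there would be no gap. Severity is minor: an exploratory aim, no effect on the progression criteria, and a cheap remedy.

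**What to change.** Add the answer 'I do not have Medicare' to the CP item on Questionnaire 3. In Section 9.5, beside the planned count, report (a) the proportion of responders with Medicare and (b) willingness among holders, and run the opt-in versus opt-out comparison among holders. The same text should say where 'I don't know' and blank answers go, since the comparison has two groups.

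The cost is one response option in REDCap and a few lines of text. The statistical price is a smaller denominator for willingness. If all 130 answered and 40% held Medicare, there would be 130 × 0.40 = 52 holders. At 80% willing, the 95% half-width is 1.96 × √(0.80 × 0.20 / 52), about 11 points, against 1.96 × √(0.80 × 0.20 / 130), about 7 points, for all 130. The wider interval belongs to a quantity with a clear meaning, and the planned count is still reported.
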